#### **Randomization and Masking**

Eligible patients were randomly assigned utilizing a computer-generated mixed block size in a 1:1 ratio to receive epicardial injections of either 250 units (5 mL) of onabotulinumtoxinA (BotoxTM) or an equivalent volume of identical normal saline (placebo injection) equally amongst five identical syringes.

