#### **Outcomes**

The primary end point of this study was time to  $>30$  seconds of in-hospital POAF as assessed by continuous telemetry during the postoperative hospitalization. Pre-specified secondary end points included the incidence of POAF, and among those developing POAF the duration of first POAF episode, in-hospital burden of POAF (percent of postoperative hospitalization spent in AF), proportion of recurrent (greater than one episode lasting  $>30$ s) or prolonged (two days or greater in duration) POAF, and need for POAF treatment (medications administered for rate control, rhythm control, or electrical cardioversions for POAF). Additionally, the ICU and hospital LOS were compared between groups. As an exploratory analysis, we also examined the incidence of

hemodynamically significant new-onset POAF, resulting in rapid ventricular response (heart rate > 100 BPM) and hypotension (systolic blood pressure < 100 mmHg).

Safety end points included the incidence of any adverse event or postoperative complication, the incidence of adverse events prolonging LOS, and postoperative mortality. Additionally, duration of postoperative mechanical ventilation and the incidence of reintubation were compared between groups.

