### ***Statistical Analysis***

Based on a pilot trial showing a pronounced reduction (30 day relative risk reduction 78%) in POAF after injecting BoNTA into the epicardial fat pads, we anticipated a significant reduction in the risk for POAF with epicardial BoNTA injection in our cohort. Our study sought to include valve surgery patients, which would result in a higher-risk population for POAF. Based upon a two-tailed alpha of 0.05, an estimated POAF incidence of 40% in the control group, and a total sample size of 130 (n=65 in each arm), we prospectively determined 80% power to detect a 40% difference in relative risk (corresponding to a hazard ratio of 0.4) between treatment groups for the primary outcome.

Analyses were based on the intention-to-treat principle in all patients who received epicardial injection (modified intention-to-treat analysis). Patient characteristics were summarized by standard descriptive statistics and were compared between groups using t-tests, Wilcoxon rank sum tests, Chi-square tests, or Fisher exact tests as appropriate. The Kaplan-Meier method was used to construct non-parametric estimates of the distribution of time to first POAF event. Adjustment of treatment effect for baseline factors previously found associated with POAF outcome was accomplished using Cox proportional hazards modeling. The proportional hazards assumption was confirmed via log-log plots, plots of Schoenfeld residuals by time, and testing of a group-time interaction in the model. Secondary analyses were conducted via parametric and non-parametric assessments as appropriate.

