Secondary analysis of incidence of POAF was conducted via univariable and adjusted logistic regression with the same baseline characteristics as in the primary outcome model. Heterogeneity of treatment effect was explored in patient subgroups defined by surgery type, POAF risk as assessed by the Multicenter Study of Perioperative Ischemia (McSPI) AFRisk index, preoperative angiotensin converting enzyme inhibitor (ACEi) use, beta-blocker use, diabetes, and congestive heart failure. We studied differences in ICU and hospital LOS via Wilcoxon rank sum tests. In order to characterize severity of POAF between groups, we explored group differences among patients who developed POAF in duration of first POAF, initial ventricular rate, total POAF duration (cumulative duration of all in-hospital POAF), and total POAF burden (percent of postoperative hospital LOS spent in AF) via Wilcoxon rank sum tests. We compared the incidence of recurrent POAF, hemodynamically significant POAF, two or greater days of POAF, and need for treatment for AF via Chi-Square or Fisher exact tests. We investigated differences in the incidence of safety endpoints via Chi-Square or Fisher exact tests, and used a Wilcoxon rank sum test to explore differences in duration of postoperative mechanical ventilation.

Because multiple comparisons of secondary outcomes were performed without post-hoc adjustment of the significance level, these outcomes should be interpreted as

exploratory. All comparisons were 2-tailed and significance was set at  $p<0.05$ . Analyses were performed using SAS version 9.4 (SAS Inc., Cary, NC). A data safety monitoring board consisting of a cardiothoracic surgeon, cardiothoracic anesthesiologist, cardiac electrophysiologist, and biostatistician examined blinded, aggregate adverse event data at 10%, 25%, and 50% accrual in order to ensure adequate safety of the study.

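### Read naturally, the safety board's three reviews used pooled adverse-event data, which cannot attribute an excess to an arm, and no board review is described for the last 65 of 130 patients

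*Combined protocol and SAP*

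**What the plan says.** The last paragraph of Statistical Analysis (Combined protocol and SAP) describes "A data safety monitoring board consisting of a cardiothoracic surgeon, cardiothoracic anesthesiologist, cardiac electrophysiologist, and biostatistician", which "examined blinded, aggregate adverse event data at 10%, 25%, and 50% accrual in order to ensure adequate safety of the study". The same section plans "a total sample size of 130 (n=65 in each arm", and Randomization and Masking allocates patients "utilizing a computer-generated mixed block size in a 1:1 ratio".

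Outcomes defines what is to be watched: "Safety end points included the incidence of any adverse event or postoperative complication", together with adverse events that prolong stay and postoperative mortality. The only between-arm safety comparison described is in Statistical Analysis: "We investigated differences in the incidence of safety endpoints via Chi-Square or Fisher exact tests". It is not tied to any board review.

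The documents do not describe tables by arm (coded or open) for the board, a route by which the board could unblind, or a board review after 50% accrual.

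**The concern.** The stated purpose of the reviews is to ensure safety. In a 1:1 placebo-controlled trial, the board's main question is whether the active arm is doing worse. Patients having bypass surgery can be expected to have complications in either arm, so a pooled total mixes that background with any effect of the injection. To read a pooled total, the board needs an outside idea of the background rate; a by-arm table takes it from the randomised control group.

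What is at stake is the protection of patients still to be enrolled. On the pooled reading, the first described look at safety by arm is the trial analysis, which comes too late for them. About 32 or 33 active-arm patients enter after the last described review.

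**Working it through.** **Inputs from the documents.** Total 130, 65 per arm (Statistical Analysis, sample size); 1:1 allocation (Randomization and Masking); reviews at 10%, 25% and 50% accrual (Statistical Analysis, last paragraph); two-sided 0.05 (Statistical Analysis). The plan gives no performance figure for its safety monitoring, so there is none to reproduce.

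**Assumptions.** The documents give no adverse-event rates, so every rate below is assumed. Near-equal arms at each review are also assumed. Where the total is odd, both splits are shown. All pairs are control vs active.

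**Step 1: timing.**
- 130 × 0.10 = 13
- 130 × 0.25 = 32.5, taken as 33
- 130 × 0.50 = 65
- After the last described review: 130 − 65 = 65 patients, of whom 65/2 = 32.5, so 32 or 33, are on active treatment.

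**Step 2: what one pooled total can hide.** Take 13 events in 65 patients (13/65 = 20%). Two-sided Fisher exact p-values:

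| Control | Active | p |
|---|---|---|
| 6/32 | 7/33 | 1.0 |
| 3/32 | 10/33 | 0.061 |
| 3/33 | 10/32 | 0.033 |
| 1/32 | 12/33 | 0.0012 |
| 1/33 | 12/32 | 0.0005 |

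A board that sees only the total sees the same 13 in every row.

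**Step 3: what by-arm tables would add.** Power is the sum, over all pairs of counts with Fisher p < 0.05, of the product of the two binomial probabilities.

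| Patients | 10% vs 20% | 10% vs 30% |
|---|---|---|
| 13 (6+7 or 7+6) | 0.3–0.9% | 1.7–3.8% |
| 33 (16+17 or 17+16) | 6–10% | 20–26% |
| 65 (32+33 or 33+32) | 12–17% | 44–50% |
| 98 (49+49), about 75% | 19% | 63% |
| 130 (65+65) | 28% | 78% |

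The p < 0.05 cut is only a yardstick. The plan sets no such trigger for the board.

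**Step 4: what pooled tables can do.** Suppose the true rates are 10% vs 30% and the pooled count at 65 patients is tested, one-sided at 5%, against an assumed background.

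| Assumed background | Flag at or above | Chance of a flag |
|---|---|---|
| 10% | 12 events | 67–69% |
| 15% | 16 events | 20–22% |
| 20% | 19 events | 4–5% |

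The pooled signal depends heavily on the background that the board believes in. In no row does it show which arm the excess comes from.

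**The case against.** There is a fair case that this is a minor matter.

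- **The wording is ambiguous and the charter is unseen.** The text could mean totals by masked group, which would show an imbalance. A charter could also let the board request by-arm data or hold extra reviews. This stands: the point concerns what is described. A reader might infer that the board had no access to arms, or that the second half of the trial went unmonitored. One sentence in a short methods summary supports neither.
- **Pooled data are not useless.** Against a 10% background, the pooled test in Step 4 flags more often (67–69%) than the by-arm test at the same review (44–50%). This stands, and it rules out the inference that the board could not have noticed a problem. The advantage disappears if the background is taken as 15% or 20%, and a pooled flag never identifies the arm.
- **By-arm tables in so small a trial detect little.** This also stands. Even at 98 patients, power for 10% vs 20% is 19%. By-arm tables should not be presented as a reliable alarm.
- **The text is in the past tense, so conduct may be finished.** If so, only the reporting advice below applies. The document does not itself claim that the board reviews showed the arms to be equally safe, and it compares safety between arms separately.
- **Pooled review is a design choice.** Nothing in the documents contradicts it. It is nevertheless a weaker choice for the stated purpose, and the alternative is cheap.

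**Conclusion.** The point holds as a limited criticism of interim safety monitoring. On the natural reading, the three described reviews, at about 13, 33 and 65 patients, could not attribute an excess of adverse events to an arm. On either reading, no board review is described for the remaining 65 patients, half of the planned total.

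The final safety analysis and the primary analysis are unaffected. The attribution part rests on reading the data as pooled; if masked groups were used, only the absence of a described late review remains. The size of the loss rests on assumed event rates. The pooled-total example shows that attribution is lost whatever the rates, while the power figures show that restoring it would give only a modest chance of a formal signal. This is a worthwhile low-cost improvement if accrual is open, and a reporting clarification if it is not.

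**What to change.** **If the plan can still be changed.** At the stated reviews, give the board adverse-event and mortality tables by coded arm (A/B, decodable at the board's request) in closed session. Have them prepared by someone outside the blinded trial team, and keep investigators blinded. One further review in the second half of accrual, for example at about 75% (130 × 0.75 = 97.5 patients), is an optional addition. Decide openly whether POAF appears in these tables: including it discloses the primary outcome to the board, and excluding it removes an arrhythmia signal.

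**Cost.** A wording change, the by-arm tables and, if adopted, one more table run; no extra patients or procedures, and no change to alpha, sample size or the primary analysis. The downsides are that the board holds by-arm safety data and that someone outside the trial team must handle the allocation codes. The documents do not say who could do that. The board's biostatistician is one candidate, but would then prepare the tables as well as review them.

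**If conduct is complete.** State whether the tables were pooled or by masked group, state that the last described review was at 50% accrual, and do not rely on the board reviews as evidence of between-arm safety. The cost is wording only.
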